5.1.2. Screening Period

For all participants, the screening period is defined as the period from informed consent to the first administration of treatment. For some variables, such as data from scans, data are allowed prior to the date of informed consent provided the procedures met the protocol-specified criteria. For some variables, data from more than one assessment within the screening period can be collected prior to the first administration of treatment. The baseline value for a variable is defined as the last non-missing value collected before the first administration of treatment.

Assessments carried out on day of first administration of treatment are considered to have taken place before the first administration of treatment, except for vital signs recorded as post-dose and treatment-emergent AEs.

5.1.3. Intervention Period

Data collected at Day 1 will be assigned to the Intervention Period if post-dose is recorded on the eCRF page. Adverse events starting on Day 1 (unless specified as starting before the dosing time), post-dose vital signs, and medications starting on Day 1 will be assigned to the Intervention Period.

The Intervention Period is defined as the period from the date / time of the first administration of treatment up to the Day 91 clinic visit. The short-term follow-up period is defined from after the Day 91 visit up to and including the earliest of 6 months after the first administration of treatment, development of unequivocal metastatic prostate cancer or until the start of new therapy, such as ADT. The long-term follow-up period will be defined for participants who have a PSA response in the first 6 months for an additional 18 months up to 24 months after the first administration of treatment, or until the start of new therapy such as ADT or development of unequivocal metastatic prostate cancer.

5.1.4. Visit Windows

Tables 5 to 7 provides the relative study day ranges to be applied to the assessment / sample collection date to derive the analysis timepoint for by timepoint analyses of PSA / laboratory / vital signs and symptom-directed physical examination.

The following considerations are to be followed when deriving the analysis timepoints:

- The relative day number of the assessment lies between the lower and upper boundary of the visit window (the boundary values are included)
- Both scheduled and unscheduled assessments are included for visit windowing
- If there are two or more valid assessments for a defined window the following rules will be applied:
 - Assessments with missing data and assessments marked “Not Done” will be considered as providing a missing response and are not permitted to be assigned to a visit window.
 - The worst value (e.g. out of reference range preferred to within range; abnormal preferred to normal) will be used in each window. If multiple assessments fall within the same window with equal value, then the first non-missing value will be used for the summary.
- Participants who have an optional third dose of MVA-PCAQ due to an initial PSA response followed by progression will have an additional day 57, 64 and 71 visit. If two assessments are in both the additional day 64 and day 91 visit window or day 71 and day 91 visit window then the first assessment will be assigned to day 64 or 71 and the second to day 91. If only one assessment is available in both windows then this will be assigned to day 91.
- Participants who have had a study pause will not have visit windowing applied for visits after this window and will have analysis visit assigned based on the recorded visit name in the eCRF.

Table 4: Definition of Visit Windows for PSA Assessments

Period	Visit	Target Day of Visit	Protocol Visit Windows	Analysis Visit Window
Screening	Screening	Day -1 ^a	Day -43 to -1	Not Applicable
Intervention	Baseline	Day 1 ^a	Day 1 ^a	Prior to or on Day 1 ^a
Intervention	Day 29	Day 1 ^b	Day 1 ^b	Day 1 ^b
Intervention	Day 57	Day 1 ^c	Day 1 ^c	Day 1 ^c
Intervention	Day 64	Day 8 ^c	Day 5 to 9 ^c	Day 2 to 14 ^c
Intervention	Additional Day 57	Day 1 ^d	Day 1 ^d	Day 1 ^d
Intervention	Additional Day 64	Day 8 ^d	Day 5 to 9 ^d	Day 2 to 14 ^d
Intervention	Day 91	Day 91 ^a	Day 89 to 91 ^a	Day 78 to 104 ^a
Short-Term Follow-Up	Month 4	Day 120 ^a	Day 113 to 127 ^a	Day 105 to 135 ^a
Short-Term Follow-Up	Month 5	Day 150 ^a	Day 143 to 157 ^a	Day 136 to 165 ^a
Short-Term Follow-Up	Month 6	Day 180 ^a	Day 173 to 187 ^a	Day 166 to 195 ^a
Long-Term Follow-Up	Month 7	Day 210 ^a	Day 203 to 217 ^a	Day 196 to 225 ^a
Long-Term Follow-Up	Month 8	Day 240 ^a	Day 233 to 247 ^a	Day 226 to 255 ^a
Long-Term Follow-Up	Month 9	Day 270 ^a	Day 263 to 287 ^a	Day 256 to 285 ^a
Long-Term Follow-Up	Month 10	Day 300 ^a	Day 293 to 307 ^a	Day 286 to 315 ^a
Long-Term Follow-Up	Month 11	Day 330 ^a	Day 323 to 337 ^a	Day 316 to 345 ^a
Long-Term Follow-Up	Month 12	Day 360 ^a	Day 353 to 367 ^a	Day 346 to 400 ^a
Long-Term Follow-Up	Month 14	Day 420 ^a	Day 413 to 427 ^a	Day 401 to 440 ^a
Long-Term Follow-Up	Month 16	Day 480 ^a	Day 473 to 487 ^a	Day 441 to 509 ^a
Long-Term Follow-Up	Month 18	Day 540 ^a	Day 533 to 547 ^a	Day 510 to 569 ^a
Long-Term Follow-Up	Month 20	Day 600 ^a	Day 593 to 607 ^a	Day 570 to 629 ^a
Long-Term Follow-Up	Month 22	Day 660 ^a	Day 653 to 667 ^a	Day 630 to 689 ^a
Long-Term Follow-Up	Month 24	Day 720 ^a	Day 713 to 727 ^a	Day 690 to 749 ^a

^a Relative to first dose of treatment

^b Relative to second dose of treatment

^c Relative to third dose of treatment

^d Relative to optional fourth dose of treatment

Table 5: Definition of Visit Windows for Laboratory Assessments

Period	Visit	Target Day of Visit	Protocol Visit Windows	Analysis Visit Window
Screening	Screening	Day -1 ^a	Day -43 to -1 ^a	Not Applicable
Intervention	Baseline	Day 1 ^a	Day 1 ^a	Prior to or on Day 1 ^a
Intervention	Day 15	Day 15 ^a	Day 12 to 16 ^a	Day 11 to 27 ^a
Intervention	Day 29	Day 1 ^b	Day 1 ^b	Day 1 ^b
Intervention	Day 36	Day 8 ^b	Day 6 to 10 ^b	Day 2 to 11 ^b
Intervention	Day 43	Day 15 ^b	Day 12 to 16 ^b	Day 11 to 27 ^b
Intervention	Day 57	Day 1 ^c	Day 1 ^c	Day 1 ^c
Intervention	Day 64	Day 8 ^c	Day 6 to 10 ^c	Day 2 to 11 ^c
Intervention	Day 71	Day 15 ^c	Day 12 to 16 ^c	Day 11 to 27 ^c
Intervention	Additional Day 57	Day 1 ^d	Day 1 ^c	Day 1 ^c
Intervention	Additional Day 64	Day 8 ^d	Day 6 to 10 ^c	Day 2 to 11 ^c
Intervention	Additional Day 71	Day 15 ^d	Day 12 to 16 ^c	Day 11 to 27 ^c
Intervention	Day 91	Day 91 ^a	Day 89 to 91 ^a	Day 78 to 104 ^a
Short-Term Follow-Up	Month 6	Day 180 ^a	Day 173 to 187 ^a	Day 166 to 195 ^a

^a Relative to first dose of treatment

^b Relative to second dose of treatment

^c Relative to third dose of treatment

^d Relative to optional fourth dose of treatment

Table 6: Definition of Visit Windows for Vital Sign Assessments/Symptom-directed Physical Examination

Period	Visit	Target Day of Visit	Protocol Visit Windows	Analysis Visit Window
Screening	Screening	Day -1 ^a	Day -43 to -1 ^a	Not Applicable
Intervention	Baseline	Day 1 ^a	Day 1 ^a	Prior to or on Day 1 ^a
Intervention	Day 15	Day 15 ^a	Day 12 to 16 ^a	Day 11 to 27 ^a
Intervention	Day 29	Day 1 ^b	Day 1 ^b	Day 1 ^b
Intervention	Day 43	Day 15 ^b	Day 12 to 16 ^b	Day 11 to 27 ^b
Intervention	Day 57	Day 1 ^c	Day 1 ^c	Day 1 ^c
Intervention	Day 71	Day 15 ^c	Day 12 to 16 ^c	Day 11 to 27 ^c
Intervention	Additional Day 57	Day 1 ^d	Day 1 ^c	Day 1 ^c
Intervention	Additional Day 71	Day 15 ^d	Day 12 to 16 ^c	Day 11 to 27 ^c
Intervention	Day 91	Day 91 ^a	Day 89 to 91 ^a	Day 78 to 104 ^a
Short-Term Follow-Up	Month 6	Day 183 ^a	Day 176 to 190 ^a	Day 121 to 457 ^a
Long-Term Follow-Up	Month 24	Day 731 ^a	Day 724 to 738 ^a	Day 458 to 738 ^a

^a Relative to first dose of treatment

^b Relative to second dose of treatment

^c Relative to third dose of treatment

^d Relative to optional fourth dose of treatment

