6.6.2. Secondary Efficacy Analysis

6.6.2.1. PSA Response to VTP-850

The number, proportion and 90% confidence intervals (CI) of participants with a confirmed PSA response, defined as a $\geq 50\%$ reduction in serum PSA compared to baseline and measured twice consecutively, at least 2 weeks apart, will be summarized by timepoint (using visit windows defined in Section 5.1) and overall for each treatment group using the EES. The proportion at each time point will present the participants who have the 1st (if confirmed at least 2 weeks later) measurement where the $\geq 50\%$ reduction in serum PSA has been met compared to baseline. Percentage change in PSA will be calculated as $100 \times (\text{PSA value (ng/ml) at visit } i - \text{PSA value at baseline}) / (\text{PSA value at baseline})$. The 90% CIs will be calculated using Jeffrey's confidence limits. The maximum percentage change in PSA from baseline will be summarized continuously by treatment group. A waterfall plot of maximum percentage change in PSA from baseline will be produced by treatment group with bars of the waterfall plot produced using different colours to represent prior radical prostatectomy or definitive external beam radiation (Yes, No). Per cohort, a spaghetti plot will display each participant's percentage change in PSA (e.g. each patient's baseline measurement will display as 100%) by the number of days since the day 1 dosing visit. On each participant's line, a marker will indicate the study day each dose occurred.

Example of this calculation of confirmed PSA response are displayed in Table 7 and Table 8.

Table 7: Calculation of PSA Response Example

Participant	Timepoint	Study Day	PSA Value (ng/mL)	PSA change from baseline	PSA absolute change from nadir	PSA percent change from nadir
1	Baseline	1	1.5			
1	Day 29	29	1.6	6.67%		
1	Day 57	57	1.0	-33.33%		
1	Day 64	64	0.9	-40.00%		
1	Month 4	122	0.8	-46.67%		
1	Month 5	153	0.2	-86.67%		
1	Month 6	164	0.2	-86.67%		
1	Month 7	215	0.3	-80.00%	0.1	50.00%
1	Month 8	246	0.3	-80.00%	0.1	50.00%
1	Month 9	271	0.5	-66.67%	0.3	150.00%

- Responder = Yes
- First observed PSA response = Month 5

- PSA progression (Defined in Section **Error! Reference source not found.**) = Month 9 (since there's a $\geq 25\%$ increase from PSA nadir AND an absolute increase of ≥ 0.2 ng/mL)
- Durable PSA response at Month 8 (Defined in Section 6.6.2.2) = Yes (since a confirmed PSA response has occurred and the criteria for PSA progression has not been met)

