Table 8: Calculation of PSA Response Example

Participant	Timepoint	Study Day	PSA Value (ng/mL)	PSA change from baseline	PSA absolute change from nadir	PSA percent change from nadir
1	Baseline	1	1.6			
1	Day 29	29	1.3	-18.75%		
1	Day 57	57	1.05	-34.38%		
1	Day 64	64	0.90	-43.75%		
1	Month 4	122	0.80	-50.00%		
1	Month 5	152	0.80	-50.00%		
1	Month 6	164	0.81	-49.38%	0.01	1.25%
1	Month 7	226	0.82	-48.75%	0.02	2.50%
1	Month 8	256	0.85	-46.88%	0.05	6.25%
1	Month 9	282	0.75	-53.13%	-0.05	-6.25%

- Responder = Yes
- First observed PSA response = Month 4
- PSA progression = No PSA progression
- Response at Month 8 = Yes (A confirmed PSA response has occurred and no PSA progression)

6.6.2.2. Durable PSA Response to VTP-850 at Month 8

If more than three participants have a confirmed PSA response at month 6 then the number, proportion and 90% CIs of participants with a durable PSA response (having a confirmed PSA response without PSA progression or on or before Month 8) will be presented for each treatment group using the EES. Participants with missing PSA data at Month 8 will have a durable PSA response imputed as described previously in Section 5.2.1. Otherwise, if participants are missing PSA data at Month 8 they will be treated as non-responders. The same summary will also be presented among participants who have a durable response at Month 6.

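### The SAP does not say whether confirmed PSA response is derived before or after its worst-value visit windowing, and its own Table 8 changes from responder to non-responder with the choice

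*SAP*

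**What the plan says.** SAP Section 5.1.4 sets the scope of the windows: study-day ranges are used "to derive the analysis timepoint for by timepoint analyses of PSA / laboratory / vital signs and symptom-directed physical examination". It adds that "Both scheduled and unscheduled assessments are included for visit windowing". For two or more valid values in one window the rule is "The worst value (e.g. out of reference range preferred to within range; abnormal preferred to normal) will be used in each window", and the first is taken only if the values are equal. No separate rule is given for PSA.

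Section 6.6.2.1 defines confirmed response as a "reduction in serum PSA compared to baseline and measured twice consecutively, at least 2 weeks apart, will be summarized by timepoint" and says that it "will be summarized by timepoint (using visit windows defined in Section 5.1) and overall for each treatment group using the EES". At each timepoint it counts participants whose first qualifying value, later confirmed, falls there.

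Table 4 gives the PSA windows: Month 4 is Days 105 to 135, Month 5 is 136 to 165, Month 6 is 166 to 195, Month 7 is 196 to 225, Month 8 is 226 to 255 and Month 9 is 256 to 285.

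Table 8 is one of two worked examples of the endpoint. It concludes that the participant is a responder with "First observed PSA response = Month 4", has no progression, and is a responder at Month 8.

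**The concern.** A confirmed response needs two consecutive low values at least 2 weeks apart. A rule that keeps one value per window, and keeps the less favourable one, can delete half of a confirming pair. Two low samples in the same window also collapse to a single record and cannot confirm each other. Worst-value selection is a sensible convention for safety laboratory tables, but here it is extended to by-timepoint PSA without saying how it interacts with an endpoint that depends on successive values.

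Responder status feeds other Phase 1 outputs. Sections 6.6.4.1 and 6.6.4.2 split the immunogenicity results by PSA response, including the ELISpot signed-rank tests. Section 6.6.2.2 produces the durable-response table only if more than three participants have a confirmed response at Month 6, so a count of four that becomes three removes the table. With about six participants per full-dose cohort, one reclassification is visible.

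**Working it through.** **Inputs.** Table 8 records with baseline 1.6 ng/mL, Table 4 windows, and the response definition in Section 6.6.2.1. Percentage change = 100 × (PSA − 1.6) / 1.6. Table 8's earlier values (Days 29, 57 and 64) are all above -50% and do not matter here.

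| Study day | Visit printed in Table 8 | Window under Table 4 | PSA (ng/mL) | Change from baseline |
|---|---|---|---|---|
| 122 | Month 4 | Month 4 | 0.80 | -50.00% |
| 152 | Month 5 | Month 5 | 0.80 | -50.00% |
| 164 | Month 6 | Month 5 | 0.81 | -49.38% |
| 226 | Month 7 | Month 8 | 0.82 | -48.75% |
| 256 | Month 8 | Month 9 | 0.85 | -46.88% |
| 282 | Month 9 | Month 9 | 0.75 | -53.13% |

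**Step 1: the SAP's printed result.** On the dated samples, Days 122 and 152 are consecutive, both at -50.00%, and 152 − 122 = 30 days apart. The response is confirmed and first seen at Month 4. The largest rise from the nadir of 0.80 is 0.85 − 0.80 = 0.05 ng/mL, below 0.2, so there is no progression. The printed result reproduces.

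**Step 2: window first, taking worst as the highest PSA.**
- Month 4: 0.80 (-50.00%).
- Month 5: the higher of 0.80 and 0.81 is 0.81 (-49.38%).
- Months 6 and 7: empty.
- Month 8: 0.82 (-48.75%).
- Month 9: the higher of 0.85 and 0.75 is 0.85 (-46.88%).

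Only Month 4 reaches -50%. There is no confirmed pair, so the participant is a non-responder and has no durable response at Month 8.

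**Step 3: other one-value-per-window rules.** Keeping the lowest, the first or the closest to target day leaves Table 8 a responder. Keeping the last makes it a non-responder.

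**Step 4: labels.** Days 164, 226 and 256 are printed as Months 6, 7 and 8, but Table 4 places them in Months 5, 8 and 9. Table 7 also prints Day 164 as Month 6. Its two Month 5 values (Days 153 and 164) are both 0.2 ng/mL, so its responder status is the same under every rule. Those two samples are 164 − 153 = 11 days apart and do not confirm each other; later samples do (Days 164 and 215 are 51 days apart).

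**Step 5: how a collision can arise.** The Month 5 window is 165 − 136 + 1 = 30 days long, and confirmation needs only 14 days. Unscheduled samples count. Illustrative case: two samples on Days 140 and 156, both below -50%, are 16 days apart but become one record.

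**Step 6: size in a cohort.** For illustration, one such change in six participants moves the response rate from 1/6 (16.7%, Jeffreys 90% CI 3.0% to 49.5%) to 0/6 (upper limit 26.4%, lower limit set to 0).

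**The case against.** The best defence is scope. Section 5.1.4 confines the windows to by-timepoint analyses, and in Section 6.6.2.1 the reference to windows is attached to the by-timepoint summary, with overall following it. Sections 2.2.2.1 and 5.2.1 define response on consecutive measurements without mentioning windows. Table 8 uses every dated sample, and its first-response month agrees with using Table 4 only to label Day 122. On that reading nothing is lost. This is probably what the authors meant, but the SAP does not state it, and the by-timepoint response table is expressly tied to the windows.

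Second, worst is framed by reference range or abnormality. If 0.80 and 0.81 have the same status, the rule as written does not choose between them. This stands: the change in Step 2 rests on an assumption. The missing direction is itself part of the gap.

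Third, collisions should be uncommon. From Month 4 on, a visit within 7 days of its target stays inside its own analysis window, and the schedule of assessments has no separate confirmatory draw. Table 8's Days 164, 226 and 256 lie outside their protocol windows and may simply be careless invented days. A later scheduled sample may also confirm a response that windowing had broken. All of this stands and limits the frequency, which the documents do not allow one to estimate.

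A reader might infer that windowing delays progression and so flatters durability. The documents do not support one direction. Keeping the highest value can raise the nadir, but it can also retain a high value that meets the progression criterion sooner. Neither worked example changes its progression result.

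**Conclusion.** The gap is real and of moderate severity. Under the assumption that worst means highest PSA, a stated SAP rule contradicts one of its two worked examples, and by-timepoint and overall response can disagree for the same participant. Without that assumption, the rule for choosing between two PSA values in a window is undefined. The mislabelled visits in Tables 7 and 8 are an inconsistency on any reading. In practice the effect is limited to participants with an off-window or unscheduled PSA sample.

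A reader might also infer that this puts the Stage 1 rule of at least 4 responders in 25 at risk. That goes too far. This SAP covers Phase 1 only and says that Phase 2 will have its own plan. The protocol defines response for that rule on consecutive timepoints without analysis windows (Sections 4.1.2 and 11.4), and the Safety Monitoring Committee makes the decision. Phase 1 contributes 6 of the 25. The chance of exactly four responders would only describe being at the boundary; a wrong decision would also need one of the four to be misclassified. Nor does the point touch the primary objective, which is safety.

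**What to change.** - In Section 5.1.4, state that the worst-value rule does not apply to PSA.
- In Section 6.6.2, state that confirmed response, first-response date, nadir and progression are derived from all dated PSA samples, scheduled and unscheduled. Say how consecutive is read when neighbouring samples are less than 2 weeks apart, as on Days 153 and 164 in Table 7.
- Use the Table 4 windows only for by-visit display, with a prespecified PSA selection rule such as the value closest to the target day. Assign a confirmed response to the window that contains its first qualifying sample.
- Correct the visit labels or the study days in Tables 7 and 8 so that they agree with Table 4.
- Carry the same wording into the Phase 2 SAP.

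The cost is SAP text and the programming specification. No new data are needed, and Table 8 can serve as a test case for the program.

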| Immunogenicity assessments | | | | | | | | |
| Blood for PBMC assessment ^f | | | | | X | X | | |
| Blood for anti-antigen antibody assessment | | | | | X | X | | |

Abbreviations: AESIs- Adverse Events of Special Interest, d=days, EOT=End of Trial, PBMC=peripheral blood mononuclear cells, PSA=prostate-specific antigen, PSMA=prostate-specific membrane antigen

^a Participants will only have 1 EOT visit at either Months 6 or 24 or earlier in the event of initiation of new therapy (such as ADT) or development of unequivocal metastatic prostate cancer. Participants with no PSA response in the first 6 months will not enter the Long-Term Follow-up Period. Participants with a PSA response through Month 6 will enter the Long-term Follow-up Period.

^b Visits during the Follow-up Periods are from Day 1. Windows are relative to the target date of the visit.

^c If a cardiac event is reported, blood should be taken for an additional assessment of troponin T and the participant should undergo an additional ECG and echocardiogram at the earliest opportunity

^d If troponin T test result is abnormal, a re-test on the following day is required.

^e PSMA scan can be performed at any time for participants who had a positive PSMA scan prior to screening and where a 50% reduction from baseline in PSA is observed.

^fOnly required at sites qualified by Barinthus Biotherapeutics to perform PBMC isolation/processing.

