2.7. Safety Variable(s)

The planned timepoints for all safety assessments are provided in Section 1.3 of the protocol. Vital signs will include temperature, systolic and diastolic blood pressure and pulse. Blood pressure and pulse will be measured in a sitting position after 3 minutes of rest. Vital signs will be measured at Screening, Days 1, 15, 29, 43, 57, 71, 91 and Months 6 and 24. Assessments at Days 57, 71, 91 and Month 6 may be repeated for participants receiving a third dose of MVA-PCAQ after initial PSA response followed by progression or in participants whose 2nd dose of MVA was delayed due to study pause.

A complete physical examination is performed at Screening only, and a symptom-directed physical examination will be performed at Days 1, 15, 29, 43, 57, 71 and 91 and Months 6 and 24/End of Trial visit. Assessments at days 57 and 71 may be repeated for participants receiving a third dose of MVA-PCAQ after initial PSA response followed by progression or in participants whose 2nd dose of MVA was delayed due to study pause.

Scheduled clinical laboratory assessments will be performed using a central laboratory at Screening, Days 1, 15, 29, 36, 43, 57, 64, 71, 91 and Month 6. Assessments at days 57, 64 and 71 may be repeated for participants receiving a third dose of MVA-PCAQ after initial PSA response followed by progression or in participants whose 2nd dose of MVA was delayed due to study pause.

Electrocardiograms (ECGs) will be performed at Screening, Days 1, 15, 29, 43, 57, 71, 91 and Month 6. Assessments at days 57 and 71 may be repeated for participants receiving a third dose of MVA-PCAQ after initial PSA response followed by progression or in participants whose 2nd dose of MVA was delayed due to study pause.

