6.7.5. Electrocardiograms

Electrocardiogram (ECG) assessments will be taken during the study at screening, Days 1, 15, 29 (pre-dose), 43, 57 (pre-dose), 71 and 91. Assessments may be repeated for participants receiving a third dose of MVA-PCAQ after initial PSA response followed by progression or in participants whose 2nd dose of MVA was delayed due to study pause. The following assessments are collected:

- An overall investigator assessment classified as normal, abnormal, not clinically significant / abnormal, clinically significant
- Heart rate (bpm);
- PR interval (msec);
- QRS interval (msec);
- QT interval (msec);
- Fridericia corrected QT (QTcF) interval (msec)

A summary table of absolute values and percentage change from baseline for ECG heart rate, PR interval, QRS interval, QT interval and QTcF interval will be presented over time for the Safety Analysis Set. A listing of all ECG data will be provided for the Safety Analysis Set.

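### SAP Table 6 labels vital signs and examinations from Day 121 to 457 as Month 6, so the worst-value rule can replace the Day 180 reading with a much later one

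*SAP*

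**What the plan says.** SAP 5.1.4 has three window tables. In Table 6 (vital signs and symptom-directed physical examination), Month 6 has target Day 183, a stated protocol window of Day 176 to 190, and analysis window "Day 121 to 457 ^a". Month 24 has target Day 731 and analysis window Day 458 to 738. In Table 4 (PSA) and Table 5 (laboratory), Month 6 has target Day 180 and analysis window "Day 166 to 195 ^a". Protocol Table 2 puts Month 6 at Day 180 and Month 24 at Day 720, each ±7 days.

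Two rules in SAP 5.1.4 decide which reading is used. First, "Both scheduled and unscheduled assessments are included for visit windowing". Second, where several readings share a window, "The worst value (e.g. out of reference range preferred to within range; abnormal preferred to normal) will be used in each window". There is one exemption: "Participants who have had a study pause will not have visit windowing applied for visits after this window". Those men are placed by the visit name on the eCRF.

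On the schedule, SAP 2.7 says "Vital signs will be measured at Screening, Days 1, 15, 29, 43, 57, 71, 91 and Months 6 and 24", with repeats possible after an additional MVA-PCAQ dose. Protocol Table 2, footnote a, adds: "Participants will only have 1 EOT visit at either Months 6 or 24 or earlier in the event of initiation of new therapy" or of metastatic disease. Both end-of-trial columns of that table include vital signs and the symptom-directed examination.

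**The concern.** One visit has two definitions within the primary safety endpoint, which includes change from baseline in laboratory tests and vital signs at each time point (SAP 2.2.1.1). The Table 6 definition also disagrees with the protocol's own target days.

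A wide window does limited harm if the reading closest to target is used. Here the worst reading is used. A row headed Month 6 can therefore hold a value taken about nine months after that visit, chosen because it was abnormal. Two by-timepoint outputs depend on this: observed values and change from baseline for vital signs (SAP 6.7.4), and abnormalities by body system for the physical examination (SAP 6.7.6). Planned cohorts are 3 to 6 men, so one misplaced reading can visibly shift a row.

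**Working it through.** **1. Target days and protocol windows.**

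| Source | Month 6 target | Month 6 protocol window | Month 24 target |
|---|---|---|---|
| Protocol Table 2 | Day 180 | 180 ± 7 = Day 173 to 187 | Day 720 |
| SAP Table 4 | Day 180 | Day 173 to 187 | Day 720 |
| SAP Table 5 | Day 180 | Day 173 to 187 | no such row |
| SAP Table 6 | Day 183 | Day 176 to 190 | Day 731 |

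Table 6 is the odd one out.

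**2. Reproducing the windows.** The SAP states no rule, so I tried midpoints between target days.
- Tables 4 and 5: (150 + 180)/2 = 165, so the window starts at Day 166; (180 + 210)/2 = 195. Both bounds are reproduced.
- Table 6, upper bound: (183 + 731)/2 = 457. Reproduced.
- Table 6, lower bound: the preceding visit is Day 91, and (91 + 183)/2 = 137, not 121. Day 121 appears only if Day 57 is taken as the preceding visit: (57 + 183)/2 = 120. That is my inference.

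**3. Width and reach.**
- Table 6: 457 − 121 + 1 = 337 days. Tables 4 and 5: 195 − 166 + 1 = 30 days. Ratio 337/30 = 11.2.
- Latest reading: 457 − 180 = 277 days after Day 180, or 277/30.4375 = 9.1 months.
- Earliest reading: 180 − 121 = 59 days before Day 180.
- The window spans the whole PSA windows for Months 5 to 12 and Month 14, and parts of Months 4 and 16.
- The Day 91 window ends at Day 104, so Days 105 to 120 (16 days) fall in no window counted from first dose.

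**4. Who can have a second reading in the window.**
- *Exit after Month 6, by Day 457.* Possible mainly for PSA responders, since other men finish at Month 6 (protocol 4.1.4).
- *Additional MVA-PCAQ dose.* Table 6 has rows for the repeat Day 57 and Day 71 visits, but none for the repeat Month 6 visit described in SAP 2.7. The only overlap rule concerns additional Day 64 or 71 against Day 91.
- *Unscheduled visit* between Day 121 and 457.

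**5. Illustration (assumed values).** Systolic pressure is 130 mmHg at Day 180 and 165 mmHg at an exit visit on Day 400. I take Table 10 as the reference range (high is 160 mmHg or more). Under Table 6 the Month 6 row shows 165; under Day 166 to 195 it shows 130.

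**6. Exit between Day 121 and 165.** There is no later Day 180 reading, so nothing is replaced. Vital signs are labelled Month 6. The laboratory results from the same visit fall between the Table 5 windows (Day 104 and Day 166) and are assigned to no time point.

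**7. Is correcting the target days enough?** With midpoints kept and targets of 91, 180 and 720, the bounds are (91 + 180)/2 = 135.5 and (180 + 720)/2 = 450. The window would be about Day 136 to 450, or 315 days, so it would not be enough.

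**The case against.** The best defence is that vital signs have only two scheduled visits after Day 91, so a wide midpoint window is a recognisable way to keep early-exit readings in the table. The 30-day window simply reflects the monthly PSA grid. The output is descriptive and all vital signs are listed. The Phase 2 regimen is chosen on safety through the DLT period after the first booster (protocol 4.1.1), not on Month 6 vital signs. All of that stands and limits the consequence. It does not explain the target days and protocol windows that contradict the protocol, the lower bound of Day 121, or the unassigned Days 105 to 120. Nor does it justify pairing such a window with a worst-value rule.

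A reader might infer more than the documents support:
- *That every early exit competes with a Day 180 reading.* A man who leaves at Day 125 has none.
- *That a large share of the roughly 25 Phase 1 men is affected.* No exit rate is given, later exits are largely confined to responders, and study-pause participants are exempt after the pause.
- *That the chance of an abnormal Month 6 vital-sign flag about doubles.* SAP 6.7.4 plans no by-visit flag table for vital signs. Its any-post-baseline potentially clinically important (PCI) summary and worst-change summary do not use this window.
- *That ECG results are distorted too.* Table 6 does not cover ECG.

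**Conclusion.** The point holds as a labelling and consistency defect in Table 6 that should be corrected. The mismatch with the protocol and with Tables 4 and 5 is plain on the page and needs no assumption. That a later reading can replace the Day 180 value follows from SAP 5.1.4 as written. How often it will happen is unknown: it needs a second reading between Day 121 and 457 that ranks as worse, in a man not exempted by the pause rule. The number is probably small. The by-timepoint Month 6 rows for vital signs and physical examination are at risk; the overall safety conclusions and the regimen choice are not shown to be.

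There is a separate editorial slip in SAP 6.7.5, which says "Electrocardiogram (ECG) assessments will be taken during the study at screening, Days 1, 15, 29 (pre-dose), 43, 57 (pre-dose), 71 and 91" and so omits Month 6, although SAP 2.7 and protocol Table 2 schedule an ECG then. It does not follow from Table 6.

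**What to change.** In SAP Table 6:
- Month 6: target Day 180, protocol window Day 173 to 187, analysis window Day 166 to 195, as in Tables 4 and 5.
- Month 24: target Day 720, protocol window Day 713 to 727, analysis window Day 690 to 749, as in Table 4 (Table 5 has no Month 24 row).
- Show exit and additional-visit readings outside these windows in a separate *End of Trial/Additional* row, so that none is lost and none is called Month 6.

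In SAP 6.7.5, add Month 6 to the ECG time points to agree with SAP 2.7 and protocol Table 2.

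The cost is a few SAP edits and one extra table row, with no new data. The small downside is fewer readings in the Month 6 row.
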